4.6 Follow-up Period

Patients will stop taking investigational medications at Visit 19 (Week 104) and will be re-evaluated 10 weeks later.

The following procedures will be conducted:

- IVRS will be contacted to register the visit.
- AEs, potential CV event triggers (Section 6.8.1), and concomitant medications will be reviewed.
- A complete physical exam will be conducted (refer to Section 5.2.2).
- Vital signs (sitting systolic and diastolic BP and HR) will be assessed.
- 12-lead ECG will be performed.
- Body weight will be measured.
- BMI will be calculated.
- Blood samples will be collected for the following assessments:
 - Serum pregnancy test (β hCG) for all female patients, unless patient has had a hysterectomy
 - Chemistry and hematology
 - Serum calcitonin
 - Serum creatinine
 - Serum antibodies to exenatide.
- Urine will be collected for the following assessments:
 - Urinalysis
 - Urine glucose/creatinine ratio.
- Hypoglycemia episodes will be assessed.
- Patient diary will be reviewed and collected.
- Glucose meter and supplies will be collected.

5. STUDY ASSESSMENTS

The Inform Web Based Data Capture (WBDC) system will be used for data collection and query handling. The investigator will ensure that data are recorded on the eCRFs as specified in the study protocol and in accordance with the instructions provided.

The investigator ensures the accuracy, completeness, and timeliness of the data recorded and of the provision of answers to data queries according to the Clinical Study Agreement. The investigator will sign the completed eCRFs. A copy of the completed eCRFs will be archived at the study site.

5.1 Efficacy assessments

Study outcome measures are summarized in Section 8.4.

5.1.1 HbA1c

Blood samples for measurement of HbA1c will be collected according to the schedule presented in the Study Plan (Table 1 and Table 2). The instructions for collection, processing, packaging and shipping of the samples will be detailed in the lab manual.

5.1.2 Body weight

Body weight will be measured according to the schedule presented in the Study Plan (Table 1 and Table 2). The study-site staff should use a digital precision scale if possible, and record the weight in kilograms or pounds to the first decimal point (eg, 95.3 kg). The same scale should be used and the patient should wear a standard hospital-type gown or equivalent light clothing and no shoes for the body weight measurement at each visit.

5.1.3 Waist circumference

For waist circumference measurement, the study-site personnel must ensure that:

- The patient stands and the examiner places a measuring tape in a horizontal plane around the abdomen at the level of the umbilicus.
- The measuring tape is snug, but does not compress the skin, is parallel to the floor, and is not twisted.
- The measurement is taken at the end of a normal respiratory expiration.
- The measurement is recorded in centimeters to the first decimal point.
- Waist circumference will be measured according to the schedules presented in the Study Plan (Table 1 and Table 2).

5.1.4 Fasting plasma glucose

Blood samples for measurement of FPG will be collected according to the schedules presented in the Study Plan (Table 1 and Table 2). The instructions for collection, processing, packaging and shipping of the samples will be detailed in the lab manual.

5.1.5 6-point SMBG profiles

Patients will be instructed to perform 6-point SMBG profiles according to the schedule presented in the Study Plan (Table 1 and Table 2). Each separate 6-point SMBG profile encompasses 3 days, with 3 glucose measurements obtained preprandially (within 15 minutes prior to the meal) and 3 glucose measurements obtained postprandially (1.5 to 2 hours after the meal) for the 3 main meals of the day on each of the 3 days.

Patients who receive rescue therapy should be instructed to perform the 6-point SMBG after repeat FPG results confirm that rescue therapy is needed (see Section 4.2 for additional details on rescue criteria and therapy). However, the 6-point SMBG may be omitted at investigator discretion, if the investigator determines that it will be in the subject's best interest to begin rescue therapy sooner than 3 days after the confirmatory results are received.

5.1.6 Meal Tolerance Test

Liquid Meal Tolerance Tests (MTTs) are scheduled to occur at Week 0 (Visit 3), Week 28 (Visit 12) or Early Termination or Rescue, Week 52 (Visit 15), Week 104 (Visit 19) or Early Termination or Rescue. (For patients who receive rescue therapy, the MTT should be performed before the rescue treatment is initiated. Also, for patients who prematurely and permanently discontinue study medication, the MTT should be performed before study medication is discontinued. After rescue therapy is initiated or study medication is discontinued, no further MTTs are required.) A nutritional drink (eg, Ensure) will be used as a liquid meal supplement for the MTT.

The MTT visit should be rescheduled within 3 days of the visit if any of the following apply:

- Patient did not fast for at least 8 hours prior to the visit.
- Patient did not abstain from tobacco, alcohol, and caffeine for 24 hours prior to the MTT.

At Week 0/Randomization (Visit 3), study medication is to be given **AFTER** MTT is complete.

Please follow the steps below for MTT at Visit 3:

Step	Description	Starting Time Point	Ending Time Point
1	Collect urine for urinalysis.	-15 minutes	0 minutes
2	Draw the Time 0 blood sample for glucose, insulin, C-peptide, glucagon, and other laboratory tests due at the visit.	0 minutes	5 minutes
3	Administer the liquid meal supplement, starting immediately after the blood sample is drawn. Liquid meal should be consumed over 10 minutes.	5 minutes	15 minutes
4	Draw specimens for post-liquid meal glucose, C-peptide, glucagon, and insulin at 120 minutes from Time 0 blood draw.	120 minutes	125 minutes
5	Give study medication AFTER 120-minute blood draw is complete. Metformin should be taken by the subject at the next meal following completion of the MTT.	125 minutes	130 minutes

At Week 28 (Visit 12) or Early Termination or Rescue, patients should delay administering oral study medication (dapagliflozin/placebo) on the morning of the visit and bring it to the study site visit. Dapagliflozin/placebo is given BEFORE administration of the liquid meal supplement. Exenatide/placebo is taken by the patient at the usual weekly scheduled time prior to the visit (or can be taken at the site if the patient is due for a dose at the time of the visit). Metformin should be taken by the subject at the next meal following completion of the MTT.

Please follow the steps below for MTT at Visit 12:

Step	Description	Starting Time Point	Ending Time Point
1	Give dapagliflozin/placebo (and exenatide/placebo, if applicable) 1 hour BEFORE drawing the blood sample.	-60 minutes	-55 minutes
2	Collect urine for urinalysis.	-15 minutes	0 minutes
3	Draw the Time 0 blood sample 60 minutes AFTER administration of dapagliflozin/placebo. Samples should be drawn for glucose, insulin, C-peptide, glucagon, plasma dapagliflozin/placebo, and other laboratory tests due at the visit.	0 minutes	5 minutes
4	Administer the liquid meal supplement, starting immediately after the Time 0 blood samples are drawn. Liquid meal should be consumed over 10 minutes.	5 minutes	15 minutes
5	Draw specimens for post-liquid meal glucose, C-peptide, glucagon, and insulin at 120 minutes after Time 0 (Step 3).	120 minutes	125 minutes

At Week 52 (Visit 15), Week 104 (Visit 19), or Early Termination or Rescue, patients should delay administering oral study medication (dapagliflozin/placebo) on the morning of the visit and bring it to the study site visit. Dapagliflozin/placebo is given BEFORE administration of the liquid meal supplement. Exenatide/placebo is taken by the patient at the usual weekly scheduled time prior to the visit (or can be taken at the site if the patient is due for a dose at the time of the visit). Metformin should be taken by the subject at the next meal following completion of the MTT. The MTT at Week 52 (Visit 15)/Week 104 (Visit 19)/Early Termination/Rescue will only be done on patients who have not received rescue medication.

Please follow the steps below for MTT at Visit 15, Visit 19, or Early Termination or Rescue:

Step	Description	Starting Time Point	Ending Time Point
1	Give dapagliflozin/placebo (and exenatide/placebo, if applicable) 1 hour BEFORE drawing the blood sample.	-60 minutes	-55 minutes
2	Collect urine for urinalysis.	-15 minutes	0 minutes
3	Draw the Time 0 blood sample 60 minutes AFTER administration of dapagliflozin/placebo. Samples should be drawn for glucose, insulin, C-peptide, glucagon, and other laboratory tests due at the visit.	0 minutes	5 minutes
4	Administer the liquid meal supplement, starting immediately after the Time 0 blood samples are drawn. Liquid meal should be consumed over 10 minutes.	5 minutes	15 minutes
5	Draw specimens for post-liquid meal glucose, C-peptide, glucagon, and insulin at 120 minutes after Time 0 (step 3).	120 minutes	125 minutes

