The following will be performed during these visits:

- IVRS will be contacted to register the visit.
- AEs, potential CV event triggers (Section 6.8.1), and concomitant medications will be reviewed.
- A brief physical exam will be conducted (refer to Section 5.2.2).

- Vital signs (sitting systolic and diastolic BP and HR) will be assessed.
- Body weight will be measured.
- Blood samples will be collected **prior to administration of study medication** for the following assessments:
 - Chemistry and hematology
 - HbA1c (Visits 6, 7, 8, 9, 10, and 11 only)
 - Fasting plasma glucose will be collected at all treatment visits (need for rescue will be evaluated at Visits 7 to 11 only)
 - Serum creatinine (calculated creatinine clearance; Cockcroft-Gault formula)
 - Serum antibodies to exenatide (Visits 6, 7, 8, and 10 only)
 - Plasma exenatide and dapagliflozin (Visits 6, 7, 8, and 10 only).
- Urine will be collected for the following assessments:
 - Urinalysis
 - Urine glucose/creatinine ratio
 - Pregnancy test for all female patients, unless patient has had a hysterectomy.
- Patient diary will be reviewed.
- Visit 11 only: Patients will be instructed to perform 6-point SMBG on any 3 days in the week prior to Visit 12.
- Hypoglycemia episodes will be assessed.
- Diet and exercise counseling will be provided.
- Glucose meter and supplies will be provided.
- Study medication compliance will be reviewed.
- Study medication will be dispensed every 4 weeks during the treatment period: Visits 6 to 11. Study site personnel will monitor administration of injectable study medication (if the patient is due for an injection at the time of the visit).

- Instructions, reminders, and supplies (as appropriate) will be given to the patient (or designated caregiver) for proper transportation and storage of the study medication (to ensure temperature control, etc.).
- Rescue medication will be dispensed at Visits 7 to 11 if criteria for rescue medication are met (refer to [Table 3](#)).
- Used/unused study medication will be collected every 4 weeks (Visits 6 to 11).

4.2.2 End of Treatment Period Visit (Visit 12, Week 28) or Early Termination or Rescue during Treatment Period

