Prior to this visit, patients are to have fasted overnight (at least 8 hours), and to have abstained from strenuous exercise, alcohol, tobacco, and caffeine for 24 hours. Patients should delay administering the morning dose of metformin and study medication on the morning of the visit and bring OAD medication and study medication to the study-site visit.

The following procedures will be conducted:

- IVRS will be contacted to register an End of Treatment Period Visit or Early Termination visit; the IVRS will not be contacted for a Rescue visit.
- AEs, potential CV event triggers (Section [6.8.1](#)), and concomitant medications will be reviewed.
- A complete physical exam will be conducted (refer to Section [5.2.2](#)).
- Vital signs (sitting systolic and diastolic BP and HR) will be assessed.
- 12-lead ECG will be performed **prior to administration of study medication**.
- Body weight will be measured.
- BMI will be calculated.
- Waist circumference will be measured.
- Urine will be collected for the following assessments (to be collected right before time 0 of the meal tolerance test):
 - Urinalysis
 - Urine glucose/creatinine ratio.

- Meal tolerance test will be performed (refer to Section 5.1.6). (For patients who receive rescue treatment, the MTT should be performed before the rescue treatment is initiated. Also, for patients who prematurely and permanently discontinue study medication, the MTT should be performed before study medication is discontinued. After rescue therapy is initiated or study medication is discontinued, no further MTTs are required.)
- Blood samples will be collected after **administration of dapagliflozin** for the following assessments:
 - Serum pregnancy test (β hCG) for all female patients, unless patient has had a hysterectomy
 - Chemistry and hematology
 - Serum calcitonin
 - HbA1c
 - Fasting plasma glucose (need for rescue will be evaluated; part of meal tolerance test)
 - Fasting serum lipid concentrations (total cholesterol, LDL cholesterol, HDL cholesterol, non-HDL cholesterol, and triglycerides)
 - Fasting glucagon
 - Serum creatinine (calculated creatinine clearance; Cockcroft-Gault formula)
 - Fasting C-peptide (part of meal tolerance test)
 - Fasting insulin (part of meal tolerance test)
 - Serum antibodies to exenatide
 - Plasma exenatide and dapagliflozin. Samples for plasma dapagliflozin will be drawn 1 hour after administration of study medication as part of the meal tolerance test (refer to Section 5.1.6).

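### Week 28 FPG is drawn 60 minutes after the tablet but baseline and Weeks 1 to 24 before it, so combination versus EQW may include an acute dapagliflozin effect of unknown size

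*Protocol*

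**What the plan says.** **Baseline (Visit 3).** Section 5.1.6: "At Week 0/Randomization (Visit 3), study medication is to be given AFTER MTT is complete". The last step for that visit repeats the order: "Give study medication AFTER 120-minute blood draw is complete". Baseline glucose is therefore a pre-dose value, after a placebo lead-in.

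**Weeks 1 to 24 (Visits 4 to 11).** Section 4.2.1: "Blood samples will be collected prior to administration of study medication for the following assessments". FPG is on that list: "Fasting plasma glucose will be collected at all treatment visits (need for rescue will be evaluated at Visits 7 to 11 only").

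**Week 28 (Visit 12), Early Termination and Rescue.** Section 4.2.2 reverses the order: "Blood samples will be collected after administration of dapagliflozin for the following assessments". Its list includes "Fasting plasma glucose (need for rescue will be evaluated; part of meal tolerance test"). Section 5.1.6 fixes the interval: "Draw the Time 0 blood sample 60 minutes AFTER administration of dapagliflozin/placebo", with the liquid meal given after that draw. Section 4.5 and the later steps in Section 5.1.6 apply the same order at Weeks 52 and 104.

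**Treatment and endpoints.** Under Section 1.3 the EQW arm takes a dapagliflozin placebo tablet. Section 8.5.2 lists seven secondary endpoints under multiplicity control. Two of them are FPG change to Week 28 and FPG change to Week 2, the latter for the combination against EQW only. HOMA-B and HOMA-S at Week 28 are exploratory (Section 8.4.3).

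**The concern.** FPG means a pre-dose value at eight consecutive treatment visits and a one-hour post-dose value at the visit that is formally tested. The protocol neither explains the change nor adjusts for it. Dosing before the meal has an evident purpose for the 2-hour postprandial glucose, but the same Time 0 draw also supplies FPG and fasting insulin.

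The consequence is not symmetric across arms. An hour before the Week 28 draw, patients on the combination or on dapagliflozin alone take active drug and EQW patients take placebo. Any acute lowering would enter one side of the combination-versus-EQW contrast. The two FPG secondary endpoints look like one measure at two times, but an early-versus-late reading of them is mixed up with dose-to-draw time. No statistical analysis plan could recover this later, because no pre-dose FPG is scheduled at Week 28.

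**Working it through.** **1. Sampling order side by side**

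| Visit | FPG relative to tablet | Protocol section |
|---|---|---|
| Visit 3 (baseline) | before | 4.1.4, 5.1.6 |
| Visits 4 to 11 (Weeks 1 to 24) | before | 4.2.1 |
| Visit 12 (Week 28), Early Termination, Rescue | 60 minutes after | 4.2.2, 5.1.6 |
| Visits 15 and 19 (Weeks 52 and 104) | 60 minutes after | 4.5, 5.1.6 |

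**2. Does exposure differ between the two states?** Section 1.1 gives a dapagliflozin half-life of 12.5 hours. In a one-compartment model at steady state with instant absorption, the 24-hour level is 2^(−24/12.5) = 0.26 of peak. The 1-hour level relative to the pre-dose level is 2^(−1/12.5) / 2^(−24/12.5) = 3.6. With first-order absorption at assumed rates of 0.5 to 4 per hour, the ratio is 1.9 to 3.5. Drug concentration therefore differs materially between the two sampling times. How far fasting glucose moves within that hour cannot be derived from the protocol.

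**3. Number per arm.** Section 8.2 states 209 per group for an HbA1c difference of 0.35% with SD 1.1%, 90% power and a 5% test. The two-sample t-test solution is 208.54, rounded up to 209, and 209/0.95 = 220 after 5% drop-out. The plan's figure reproduces. It is used below only as n and is not affected by this point.

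**4. Illustration for combination versus EQW.** Assumptions, none from the protocol: SD of FPG change 35, 45 or 55 mg/dL; extra one-hour lowering d of 0 to 5 mg/dL; no pre-dose difference between the arms; one unadjusted two-sided 5% test.

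SE = SD × √(2/209), which gives 3.42, 4.40 and 5.38 mg/dL.

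Rejection probability = Φ(−1.96 + d/SE) + Φ(−1.96 − d/SE).

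| d (mg/dL) | SD 35 | SD 45 | SD 55 |
|---|---|---|---|
| 0 | 5.0% | 5.0% | 5.0% |
| 1 | 6.0% | 5.6% | 5.4% |
| 2 | 9.0% | 7.4% | 6.6% |
| 3 | 14.2% | 10.5% | 8.6% |
| 5 | 30.9% | 20.6% | 15.3% |

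Worked case: with d = 5 and SD 35, d/SE = 5/3.42 = 1.46, so Φ(−0.50) + Φ(−3.42) = 0.309.

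**5. Combination versus dapagliflozin alone.** Both arms take the active tablet on the same clock, so a common acute effect largely drops out of the difference.

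**The case against.** A reader might infer that the Week 28 FPG comparison is shown to be biased, with an inflated type I error. The protocol does not support that, for several reasons.

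- It gives no one-hour effect on fasting glucose in patients already on daily dapagliflozin and still fasting. That effect could be negligible, and at d = 0 the test keeps its 5% level.
- Pairing a pre-dose baseline with a post-dose Week 28 value does not itself create a difference between arms. No arm has had active drug at baseline, and all arms follow the same blinded clock at Week 28.
- The endpoint is worded only as change in FPG to Week 28. It does not say trough or pre-dose. A lower glucose one hour after the assigned tablet is a real effect of the regimen, so the issue is what the endpoint measures and whether it is consistent.
- The illustration ignores the HbA1c gate and the adjustment across 13 secondary comparisons. It also assumes no pre-dose difference, although Section 1.1 describes dapagliflozin as lowering FPG. The likelier consequence is an overstated estimate rather than a false positive.
- Section 8.5.2 allows either a repeated-measures model or ANCOVA. Mixing of pre- and post-dose visits arises only with the former, and a treatment-by-week model gives Week 28 its own mean.
- Rescue in the treatment period needs a confirmatory repeat FPG (Table 3), so one Visit 12 value does not decide it.

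All of this stands and limits the claim. It does not remove the change of dosing state at the tested visit, which falls differently on the combination and EQW arms and carries no stated rationale. That the post-dose order is specified consistently across Sections 4.2.2, 4.5 and 5.1.6 shows it was intended for the meal test. It does not show that it suits FPG.

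**Conclusion.** The point holds as one of endpoint definition. FPG is a pre-dose measure through Week 24 and a 60-minute post-dose measure from Week 28. The Week 28 combination-versus-EQW contrast, and the related fasting insulin and HOMA measures, may include an acute dapagliflozin effect that would favour the combination. The Week 2 and Week 28 FPG endpoints are not measured in the same state.

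The size is unknown. The range of 5% to about 31% rests wholly on the assumed SD of 35 to 55 mg/dL, an assumed extra lowering of 0 to 5 mg/dL, no pre-dose difference, and an unadjusted test. It shows what could be at stake and is not an estimate of error in this trial. The comparison with dapagliflozin alone is largely unaffected. The primary HbA1c endpoint and the sample size are not touched.

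**What to change.** - In Sections 5.1.6, 4.2.2 and 4.5, draw one tube for FPG and fasting insulin on arrival, before step 1 (the tablet), and base the FPG and HOMA endpoints on it. Keep the 60-minute post-dose Time 0 sample for the meal test and the pharmacokinetic measurement.
- For patients already past Week 28, state that their value is post-dose. Record the dosing state of every FPG sample.
- Add the Week 24 FPG comparison, which is pre-dose and already collected, as a supportive analysis.
- If the sponsor prefers to keep the post-dose draw, state that definition and justify it.
- For rescue, reconcile Section 4.2 (Table 3) and Sections 4.2.1, 4.2.2, 4.5 and 5.1.6 on the dosing state of the FPG used. Table 3 applies one FPG threshold from Visit 10 through Visit 12, with pre-dose samples at Visits 10 and 11 and a post-dose sample at Visit 12. Section 4.5 also attaches a rescue check to FPG, while Tables 4 and 5 use HbA1c. Which rule applies is for the sponsor to settle.

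The cost is one extra tube at visits where patients already arrive fasting with the tablet withheld, plus a protocol and laboratory-manual amendment with the approvals that Section 10.5 requires. The real drawback is timing. This edition is dated September 2015 and first enrolment was planned for the third quarter of 2014, so a change now could leave Week 28 sampling mixed across patients. That is why the dosing state should be recorded and the Week 24 comparison added.

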5.2 Safety assessments

The investigator will evaluate all Screening and safety laboratory reports and will sign and date the review. Any out of range laboratory results should be assessed for clinical significance, and reported as AEs accordingly. The investigator should follow all clinically significant laboratory abnormalities occurring during the study that were not present at baseline. These abnormalities should be evaluated with additional tests, if necessary, until the underlying cause is diagnosed or resolution occurs. The diagnosis and resolution date must be reported to the Sponsor.

Samples will be collected according to the schedules presented in the Study Plan ([Table 1](#) and [Table 2](#)). The instructions for collection, processing, packaging and shipping of the samples will be detailed in the lab manual.

5.2.1 Laboratory safety assessments

5.2.1.1 Hematology

Hematology assessments will include the following: red cell count, hemoglobin, hematocrit, white cell count, platelets, differential count, mean cell volume, mean corpuscular hemoglobin, and mean corpuscular hemoglobin concentration (or other routine hematology assessments as approved by the Sponsor).

5.2.1.2 Chemistry

Chemistry assessments will include the following: urea nitrogen, creatinine, total protein, albumin, uric acid, TB, alkaline phosphatase (ALP), ALT, AST, gamma glutamyl transpeptidase, amylase, lipase, creatine phosphokinase (CPK), creatine kinase, muscle and brain (CK-MB) (if CPK is elevated), troponin T (if CK-MB is elevated), sodium, potassium, chloride, bicarbonate, magnesium, phosphorus, and calcium (or other routine chemistry panels as approved by the Sponsor). Fasting C-peptide will be assessed according to the schedule presented in the Study Plan ([Table 1](#) and [Table 2](#)).

